### 13.3.2 Expediting Reporting Requirements of SAEs and UPs by Site Investigators

#### 13.3.2.1 *Criteria for Reporting SAEs/UPs to the Coordinating Center*

Serious Adverse Events meeting the criteria specified below will be reported to the Coordinating Center within **24 hours** of notification that the event occurred.

Adverse events that require expedited reporting include:

- AEs or SAEs that meet the definition of an unanticipated problem
- All deaths that occur within 30 days of active treatment
- All deaths that occur after 30 days of active treatment that are unexpected and possibly, probably, or definitely related to the study agent or procedure
- All serious adverse events, regardless of relationship to study agent or study procedure, that occur within 30 days of the last day of treatment
- All serious adverse events that occurred after 30 days of active treatment/therapy that are considered possibly, probably, or definitely related to the study agent or procedure

Note: Follow-up reports must be submitted for all events that require expedited reporting when the status of the event changes and until the resolution or stabilization of the event.

Reportable serious adverse events must be followed until the event is resolved, stabilized, or determined to be irreversible by the participating investigator; for ongoing reportable adverse events that are unrelated to study agent, the follow-up period may end at the 30-days post study-drug assessment. The Coordinating Center should be consulted prior to ending the follow-up of events that have stabilized.

### 13.3.3 SAE Reporting to Local IRB

#### 13.3.3.1 *Non COH Sites: Procedure for Reporting SAEs/UPs to the COH Data Coordinating Center*

1. Sites are to report to their local IRB per their sites' specific institutional and IRB guidelines. As soon as possible, non-COH sites will provide to the COH Data Coordinating Center copies of the IRB submission and corresponding IRB response.
2. Document/describe the SAE/UP on each of the following:
  - a. MedWatch 3500A
    - i. Downloadable form at <http://www.fda.gov/medwatch/getforms.htm>
  - b. UP/SAE Coversheet
    - i. SAE Coversheet is found in [Appendix 6](#). A modifiable Microsoft Word document is also available from the Data Coordinating Center. An electronic signature on the document will be accepted.
3. Scan and email above documents to [contact] with the subject title as "15334 SAE".
  - a. All SAE reports received at this account are forwarded immediately to study Principal Investigator, and to Coordinating Center personnel.
  - b. While not required, if available and applicable, please also include the local IRB submission for this event in the submission.

4. If an email receipt from Coordinating Center personnel is not received within one working day, please call [contact] and/or email [contact].

#### 13.3.3.2 COH Investigative Sites: Procedure for Reporting SAEs/Ups to the Coordinating Center

1. Email the following information to [contact] and [contact].
  - a. Participant ID, date the event met criteria for reporting, whether the event meets the definition of serious, whether the event is an unanticipated problem, grade of event, attribution of event, whether the event is a known expected toxicity to study agent.
2. Complete the iRIS AE/UP reporting form per COH reporting timeline.

#### 13.3.4 Additional Reporting Requirements of the Study Principal Investigator

##### 13.3.4.1 *Reporting to COH IRB and DSMC*

The study PI (or designee) will report to COH IRB and DSMC via iRIS all reportable serious adverse events that occur at COH and non-COH sites and meet COH IRB and DSMC expedited reporting criteria and occur at non-COH sites according to [City of Hope's Institutional policy](#). The study PI will also submit a [Protocol Management Team \(PMT\) report](#) to the COH DSMC at the frequency outlined in [Section 15.6](#). this report will include a review of aggregate adverse event data.

##### 13.3.4.2 *Reporting to the FDA*

The study PI (or designee) will be responsible for contacting the Office of IND Development and Regulatory Affairs (OIDRA) at COH to ensure prompt reporting of safety reports to the FDA. OIDRA will assist the PI with the preparation of the report and submit the report to the FDA in accordance with the approved [City of Hope's Institutional policy](#).

Serious Adverse Events meeting the requirements for expedited reporting to the Food and Drug Administration (FDA), as defined in [21 CFR 312.32](#), will be reported as an IND safety report using the [MedWatch Form FDA 3500A for Mandatory Reporting](#).

The criteria that require reporting using the Medwatch 3500A are:

- Any unexpected fatal or life threatening adverse experience associated with use of the drug must be reported to the FDA no later than 7 calendar days after initial receipt of the information [\[21 CFR 312.32\(c\)\(2\)\]](#)
- Any adverse experience associated with use of the drug that is both serious and unexpected must be submitted no later than 15 calendar days after initial receipt of the information [\[21 CFR 312.32\(c\)\(1\)\]](#)
- Any follow-up information to a study report shall be reported as soon as the relevant information becomes available. [\[21 CFR 312.32\(d\)\(3\)\]](#)

In addition, the study PI will submit annually within 60 days (via COH OIDRA) of the anniversary date of when the IND went into effect, an annual report to the FDA which is to include a narrative summary and analysis of the information of all FDA reports within the reporting interval, a summary report of adverse drug experiences, and history of actions taken since the last report because of adverse drug experiences.

##### 13.3.4.3 *Reporting to Participating Investigators*

The study PI (or designee) will report all reportable serious adverse events to participating investigators as an IND Safety Report occurring within 30 calendar days of receipt of sponsor (lead site) notification, and indicate whether or not a protocol and/or consent form change is required. A cover letter will indicate the

protocol title, the IND#, whether the FDA was informed, and, for non-COH sites, a statement that the report should be submitted to their local IRB for review as an IND safety report if applicable per local IRB policy.

The study PI will also forward to participating sites all IND safety reports received from Pharmacyclics, indicating whether a consent form or protocol change is required within 30 days of notification to study PI.

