#### 13.1.4 Adverse Events of Special Interest (AESI)

Specific adverse events, or groups of adverse events, will be followed as part of standard safety monitoring activities. These events (regardless of seriousness) will be reported to Pharmacyclics Drug Safety per SAE reporting timelines.

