## 13.3 Reporting of Adverse Events

### 13.3.1 Routine reporting of Non-Serious Adverse Events by Site Investigators

AEs will be collected from the signing of informed consent until ending study participation. Routine AE reporting will occur via data entry into the study eCRF. AEs will be monitored by the Protocol Management Team (PMT). Adverse events that do not meet the criteria of serious OR are not unanticipated problems do not require expedited reporting. AEs reported through expedited processes (i.e. reported to the IRB, DSMC, FDA, etc.) must also be reported in routine study data submissions.

AEs recorded in the eCRF include:

- Highest Grade for all toxicities
- All SAEs

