#### 13.3.4.4 *Reporting to Pharmacyclics*

All serious adverse events and AESIs (initial and follow-up information) will be reported on FDA MedWatch (Form 3500A) or Suspect Adverse Event Report (CIOMS Form 1) IRB Reporting Form and sent via email ([[contact]](mailto:[contact])) or [contact]) by the Study PI to Pharmacyclics Drug Safety, or designee, within 15 days of the event.

The Study PI will report to Pharmacyclics summary safety information every three months.

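### Section 13.3.4.3 allows 30 days to send participating investigators safety reports that must reach the FDA in 7 or 15 days, and 30 days is longer than one treatment cycle

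*Combined protocol and SAP*

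**What the plan says.** **Notice to the FDA (Section 13.3.4.2).** An unexpected fatal or life-threatening experience associated with the drug "must be reported to the FDA no later than 7 calendar days after initial receipt of the information". An experience associated with the drug that is "both serious and unexpected must be submitted no later than 15 calendar days after initial receipt of the information" has the longer limit.

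**Notice to participating investigators (Section 13.3.4.3).** The Study PI or designee "will report all reportable serious adverse events to participating investigators as an IND Safety Report", with the limit "within 30 calendar days of receipt of sponsor (lead site) notification". The cover letter must state whether the FDA was informed and whether a protocol or consent change is needed. For IND safety reports that come from Pharmacyclics, the Study PI forwards them, "indicating whether a consent form or protocol change is required within 30 days of notification to study PI".

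**Notice to Pharmacyclics (Sections 13.1.4 and 13.3.4.4).** Major hemorrhage is an AESI. On AESIs, Section 13.1.4 says: "These events (regardless of seriousness) will be reported to Pharmacyclics Drug Safety per SAE reporting timelines". Section 13.3.4.4 has the Study PI send SAEs and AESIs "within 15 days of the event".

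**Notice from sites to the lead site (Sections 13.3.1 and 13.3.2.1).** The 24-hour list covers unanticipated problems (serious or not), specified deaths and specified SAEs. It does not name AESIs. Section 13.3.1 says: "Adverse events that do not meet the criteria of serious OR are not unanticipated problems do not require expedited reporting". Table 12.3.1 gives 5 business days for the routine adverse event form (a separate rule applies to transplant patients).

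**The concern.** This is a four-site trial of a combination whose joint toxicity is still being characterized. When a serious unexpected event occurs at one site, the physicians who can watch for it in other patients are the investigators at the other sites. The plan gives them the longest deadline of any recipient, and that deadline is longer than the interval between BV infusions.

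No other provision guarantees earlier notice. The Protocol Management Team includes site investigators, but Section 15.3 only recommends that it meet at least monthly. Reports to the DSMC are quarterly (Section 15.6).

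Two smaller mismatches lie in the same group of sections. AESIs are placed on SAE timelines, but no site-level route delivers them on those timelines. The Pharmacyclics clock starts at the event, whereas the site clock starts at notification and the FDA clock at receipt of the information.

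**Working it through.** The plan states deadlines here, not a calculated figure, so the check compares the deadlines and sets them against the dosing schedule.

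**Inputs**
- FDA limits: 7 and 15 calendar days (13.3.4.2).
- Investigator limit: 30 calendar days (13.3.4.3).
- BV on Day 1 of each 21-day cycle (5.1.1), with a window of ±3 days (5.1.7).
- Ibrutinib daily (5.2).
- Next cycle may start up to 3 weeks late for toxicity (6.2).

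**Step 1: lag behind the FDA.** Take both clocks to start when the lead site receives the information.
- Unexpected fatal or life-threatening events: 30 − 7 = 23 days.
- Other serious unexpected events: 30 − 15 = 15 days.

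**Step 2: treatment given elsewhere before notice is due.** For a notice window of w days and a cycle of c days, a patient receives at least floor(w/c) infusions, and at most one more when w is not a multiple of c. If patients are spread evenly over the cycle, the share reaching at least one infusion is min(1, w/c) and the mean number is w/c.

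| Cycle c (days) | Window w (days) | Infusions | Share with ≥1 | Mean |
|---|---|---|---|---|
| 21 | 7 | 0–1 | 33% | 0.33 |
| 21 | 15 | 0–1 | 71% | 0.71 |
| 21 | 30 | 1–2 | 100% | 1.43 |
| 18 (21 − 3) | 30 | 1–2 | 100% | 1.67 |
| 24 (21 + 3) | 30 | 1–2 | 100% | 1.25 |
| 42 (21 + 21) | 30 | 0–1 | 71% | 0.71 |

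At one ibrutinib dose per day, the windows allow up to 7, 15 or 30 doses. With 30 days, every on-schedule patient reaches at least one infusion, and the ±3-day window does not change that. A patient whose own cycle is delayed by three weeks may have none.

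**Step 3: route for a non-serious AESI.** Section 13.1.4 demands SAE timelines. The 24-hour list in 13.3.2.1 captures such an event only if it is also an unanticipated problem, and 13.3.1 exempts other non-serious events. A non-serious Grade 3 bleed that is not an unanticipated problem is therefore left with the routine form at 5 business days.

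**Step 4: the clock that starts at the event.** If the Study PI learns of an event more than 15 days after it happened, the report to Pharmacyclics is overdue before it can be written. This can happen under the plan's own schedule:
- From cycle 2, the study calendar (Section 9.0) shows adverse event evaluation in week 1 only. An event d days after that visit, first reported at the next one, surfaces 21 − d days later, which exceeds 15 whenever d is below 6.
- After treatment, contact is every 3 months (5.4), yet related SAEs beyond 30 days remain reportable (13.3.2.1).

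**The case against.** The strongest defense is that the clocks cover different things. The 30-day route takes all reportable SAEs, including expected and unrelated ones, and requires a view on protocol or consent changes. The FDA clocks take only unexpected, drug-associated events. Thirty days is a maximum, and nothing prevents earlier notice. In the sentence on Pharmacyclics reports, the 30 days may attach to the decision about changes and not to the forwarding.

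There are also controls on the lead-site side. SAE reports from the other sites are forwarded at once to the Study PI and coordinating center staff (13.3.3.1), and an unacceptable toxicity rate of 33% or more halts accrual (11.3). The operations plan and institutional policies are not part of these documents and may set faster site alerts.

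Most of this stands, and it supports keeping 30 days for the wider class. It does not explain why events already on a 7- or 15-day FDA clock have no shorter limit to investigators. The lead-site controls inform the lead site, not the other sites.

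Three stronger readings are tempting, and the documents do not support them:
- A reader might infer that non-serious AESIs never enter the 24-hour route. Those that are unanticipated problems do, and serious bleeds are already SAEs.
- A reader might infer that patients are re-dosed before their own physician knows. The site investigator names, grades and attributes the event (13.2). The 30-day limit concerns physicians of other patients at other sites, and the AESI gap affects the lead site and Pharmacyclics.
- A reader might infer that slow routing of non-serious unacceptable toxicities distorts the lead-in, so that all of them need 24-hour notice. Dose decisions already wait until 3 patients are fully assessed after cycle 1 (5.1.7, 11.1.2). A 24-hour rule without a cycle limit would capture such events throughout treatment.

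**Conclusion.** The concern holds as a mismatch of deadlines that should be corrected. The plan permits notice to participating investigators to trail the FDA report by up to 23 days for unexpected fatal or life-threatening events and up to 15 days for other serious unexpected ones. An on-schedule patient at another site can receive one or two BV infusions and up to 30 ibrutinib doses before notice is due. On the FDA limits, the share reaching an infusion before notice is due would fall from 100% to 71% (15 days) or 33% (7 days).

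These are maxima. They assume that both clocks start together, that notice is sent on the last permitted day, that dosing is on schedule and, for the shares, that patients are evenly spread over the cycle. The documents give no event rate, so the expected number of affected patients cannot be stated. The conclusion rests on the protocol's own deadlines, not on what outside regulations require for investigator notices.

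The AESI routing gap and the Pharmacyclics clock are real but minor. The first is confined to non-serious major hemorrhages that are not unanticipated problems. The second makes some deadlines impossible to meet, but no effect on patient safety is shown.

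**What to change.** **Main change, Section 13.3.4.3.** State that any event on the 7- or 15-day FDA clock goes to participating investigators no later than it goes to the FDA. State separately that IND safety reports received from Pharmacyclics are forwarded on a similarly short clock. Keep 30 days for all other reportable SAEs and for the decision on protocol or consent changes.

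**Minor change, Section 13.3.2.1.** Add to the 24-hour list: AESIs (Section 13.1.4), regardless of seriousness.

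**Minor change, Section 13.3.4.4.** Count the 15 days from the date the Study PI becomes aware of the event.

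The cost is wording in three subsections. For the events in the main change, a report is already being prepared for the FDA, so the extra work is sending it to the sites sooner. The AESI line adds some 24-hour notices for non-serious bleeds; the documents give no rate from which to estimate how many. No treatment rule is affected.

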#### 13.3.4.4 *Reporting to Pharmacyclics*

All serious adverse events and AESIs (initial and follow-up information) will be reported on FDA MedWatch (Form 3500A) or Suspect Adverse Event Report (CIOMS Form 1) IRB Reporting Form and sent via email ([[contact]](mailto:[contact])) or [contact]) by the Study PI to Pharmacyclics Drug Safety, or designee, within 15 days of the event.

The Study PI will report to Pharmacyclics summary safety information every three months.

### **14.0 Protocol Deviations and Single Subject Exceptions**

It is understood that deviations from the protocol should be avoided, except when necessary to eliminate an immediate hazard to a research participant. Brief interruptions and delays may occasionally be required because of travel delays, airport closures, inclement weather, family responsibilities, security alerts, government holidays, and so forth. Delays can also extend to complications of disease or unrelated medical illnesses not related to disease progression. The PI has the discretion to deviate from the protocol when necessary so long as such a deviation does not threaten patient safety or protocol scientific integrity. As a result of deviations, corrective actions are to be developed by the study staff and implemented promptly.

#### **14.1 Definitions**

##### **14.1.1 Deviation**

A deviation is a divergence from a specific element of a protocol that occurred without prior IRB approval. Investigators may deviate from the protocol to eliminate immediate hazard(s) for the protection, safety, and well-being of the study subjects without prior IRB approval.

Examples include, but are not limited to: a) dose adjustments based on excessive patient weight; b) alteration in treatment schedule due to non-availability of the research participant for treatment; and c) laboratory test results which are slightly outside the protocol requirements but at levels that do not affect participant safety.

##### **14.1.2 Single Subject Exceptions (SSE)**

An SSE is a planned deviation, meaning that it involves circumstances in which the specific procedures called for in a protocol are not in the best interests of a specific patient. It is a deviation that is anticipated and receives prior approval by the PI and the IRB.

#### **14.2 Reporting of Deviations and SSEs**

##### **14.2.1 Reporting Deviations**

For any deviation, the Study PI will notify the COH DSMC and IRB within 5 calendar days of its occurrence via [iRIS](#) in accordance with the [Clinical Research Protocol Deviation policy](#).

A list of deviations from all participating sites will be submitted along with the Protocol Management Team (PMT) progress report to the COH DSMC.

##### **For non-COH sites:**

- The local IRB and/or DSMC must be notified according to local institutional policies.

- The study Principal Investigator must be notified as soon as practical (within 24 hours of notification of the event) via email to [[contact]](mailto:[contact]) and [[contact]](mailto:[contact]). This email should provide input on the following:
  - Description of the event
  - Impact on participant safety or the safety to others
  - Impact on the study design
  - A corrective and preventative action plan

#### 14.2.2 Reporting Single Subject Exceptions

The SSE must be submitted as a “Single Subject Exception Amendment Request” via [iRIS](#) in accordance with IRB guidelines and the [Clinical Research Protocol Deviation policy](#). An IRB approved SSE does not need to be submitted as a deviation to the DSMC.

All non-emergency planned deviations from the protocol must have **prior** approval by the Study Principal Investigator, the Site Principal Investigator, COH IRB, and when applicable, the local IRB. In addition, if contractually obligated, the sponsor must also approve the deviation. Any amendments to the Protocol or Informed Consent Form must be sent to Pharmacyclics for review and approval prior to submission to the IRB.

## **15.0 Study Oversight, Quality Assurance, and Data & Safety Monitoring**

---

### **15.1 All Investigator Responsibilities**

An investigator is responsible for ensuring that an investigation is conducted according to the signed investigator statement, the investigational plan, and applicable regulations; for protecting the rights, safety, and welfare of subjects under the investigator's care; and for the control of drugs under investigation.

All Investigators agree to:

- Conduct the study in accordance with the protocol and only make changes after notifying the Sponsor (or designee), except when necessary to protect the safety, rights or welfare of subjects.
- Personally conduct or supervise the study (or investigation).
- Ensure that the requirements relating to obtaining informed consent and IRB review and approval meet federal guidelines, as stated in § 21 CFR, parts 50 and 56.
- Report to the Sponsor or designee any AEs that occur in the course of the study, in accordance with §21 CFR 312.64.
- Ensure that all associates, colleagues and employees assisting in the conduct of the study are informed about their obligations in meeting the above commitments.
- Maintain adequate and accurate records in accordance with §21 CFR 312.62 and to make those records available for inspection with the Sponsor (or designee).
- Ensure that an IRB that complies with the requirements of §21 CFR part 56 will be responsible for initial and continuing review and approval of the clinical study.
- Promptly report to the IRB and the Sponsor all changes in the research activity and all unanticipated problems involving risks to subjects or others (to include amendments and IND safety reports).
- Seek IRB and Sponsor (see Section 14) approval before any changes are made in the research study, except when necessary to eliminate hazards to the patients/subjects.
- Comply with all other requirements regarding the obligations of clinical investigators and all other pertinent requirements listed in § 21 CFR part 312.

## 15.2 Study Principal Investigator Responsibilities

The Study Principal Investigator is responsible for the conduct of the clinical trial, including overseeing that sponsor responsibilities as defined in § 21 CFR 312. Subpart D are executed in accordance with federal regulations.

